## 8.2 Populations for Analyses

- All enrolled subjects: all subjects who signed an informed consent form and were registered into the IVRS.
- All treated subjects: all subjects who received any nivolumab. This is the primary population for safety and efficacy analyses. Subpopulation analyses will be conducted for subjects in Groups 1-3.
- All response evaluable subjects: all treated subjects who have baseline and at least one on-study evaluable tumor measurement.

## 8.3 Endpoints

### 8.3.1 Primary Endpoint(s)

The primary objective of the study will be assessed by measuring the incidence for high grade (Grade 3-4 and Grade 5) IMAEs.

The IMAEs of interest are the following: skin, endocrinopathy, gastrointestinal, hepatic, renal, pulmonary, and neurologic adverse events.

### 8.3.2 Secondary Endpoint(s)

The secondary objective of the study will be assessed by measuring the following:

- median time to onset, median time to resolution of high grade (Grade 3-4) IMAEs
- percentage of subjects who received immune modulating medication (e.g. corticosteroids, infliximab, cyclophosphamide, IVIG, and mycophenolate mofetil), or hormonal replacement therapy, the percentage of subjects who received  $\geq 40$  mg prednisone equivalents, total duration of all immune modulating medications given for the IMAE and summary of subjects with resolution of AES after initiating these therapies.

[REDACTED]

- [REDACTED]
- █ [REDACTED]
- █ [REDACTED]
- █ [REDACTED]
- █ [REDACTED]
- █ [REDACTED]

## **8.4 Analyses**

### **8.4.1 Demographics and Baseline Characteristics**

Demographics, baseline disease characteristics and baseline laboratory results will be summarized using descriptive statistics for all treated subjects and all subjects in Groups 1, 2, and 3.

### **8.4.2 Primary Analyses**

The number and percentage of subjects who report high grade (Grade 3-4 and Grade 5) IMAEs will be summarized for all treated subjects. High grade (Grade 3-4 and Grade 5) IMAEs will be tabulated using worst grade per NCI CTCAE v4.0 criteria by system organ class and Medical Dictionary for Regulatory Affairs (MedDRA) preferred term.

## **9 STUDY MANAGEMENT**

### **9.1 Compliance**

#### **9.1.1 Compliance with the Protocol and Protocol Revisions**

The study shall be conducted as described in this approved protocol. All revisions to the protocol must be discussed with, and be prepared by, BMS. The investigator should not implement any deviation or change to the protocol without prior review and documented approval/favorable opinion from the IRB/IEC of an amendment, except where necessary to eliminate an immediate hazard(s) to study subjects.

If a deviation or change to a protocol is implemented to eliminate an immediate hazard(s) prior to obtaining IRB/IEC approval/favorable opinion, as soon as possible the deviation or change will be submitted to:

- IRB/IEC for review and approval/favorable opinion
- BMS
- Regulatory Authority(ies), if required by local regulations

Documentation of approval signed by the chairperson or designee of the IRB(s)/IEC(s) must be sent to BMS.

If an amendment substantially alters the study design or increases the potential risk to the subject: (1) the consent form must be revised and submitted to the IRB(s)/IEC(s) for review and approval/favorable opinion; (2) the revised form must be used to obtain consent from subjects currently enrolled in the study if they are affected by the amendment; and (3) the new form must be used to obtain consent from new subjects prior to enrollment.

If the revision is done via an administrative letter, investigators must inform their IRB(s)/IEC(s).

#### **9.1.2 Monitoring**

BMS representatives will review data centrally to identify potential issues to determine a schedule of on-site visits for targeted review of study records.

Representatives of BMS must be allowed to visit all study site locations periodically to assess the data quality and study integrity. On site they will review study records and directly compare them with source documents, discuss the conduct of the study with the investigator, and verify that the facilities remain acceptable. Certain CRF pages and/or electronic files may serve as the source documents:.

In addition, the study may be evaluated by BMS internal auditors and government inspectors who must be allowed access to CRFs, source documents, other study files, and study facilities. BMS audit reports will be kept confidential.

The investigator must notify BMS promptly of any inspections scheduled by regulatory authorities, and promptly forward copies of inspection reports to BMS.

### **9.1.2.1 Source Documentation**

The Investigator is responsible for ensuring that the source data are accurate, legible, contemporaneous, original and attributable, whether the data are hand-written on paper or entered electronically. If source data are created (first entered), modified, maintained, archived, retrieved, or transmitted electronically via computerized systems (and/or any other kind of electronic devices) as part of regulated clinical trial activities, such systems must be compliant with all applicable laws and regulations governing use of electronic records and/or electronic signatures. Such systems may include, but are not limited to, electronic medical/health records (EMRs/EHRs), adverse event tracking/reporting, protocol required assessments, and/or drug accountability records).

When paper records from such systems are used in place of electronic format to perform regulated activities, such paper records should be certified copies. A certified copy consists of a copy of original information that has been verified, as indicated by a dated signature, as an exact copy having all of the same attributes and information as the original.

### **9.1.3 Investigational Site Training**

Bristol-Myers Squibb will provide quality investigational staff training prior to study initiation. Training topics will include but are not limited to: GCP, AE reporting, study details and procedure, electronic CRFs, study documentation, informed consent, and enrollment of WOCBP.

## **9.2 Records**

### **9.2.1 Records Retention**

The investigator must retain all study records and source documents for the maximum period required by applicable regulations and guidelines, or institution procedures, or for the period specified by BMS, whichever is longer. The investigator must contact BMS prior to destroying any records associated with the study.

BMS will notify the investigator when the study records are no longer needed.

If the investigator withdraws from the study, (eg, relocation, retirement), the records shall be transferred to a mutually agreed upon designee (eg, another investigator, IRB). Notice of such transfer will be given in writing to BMS.

### **9.2.2 Study Drug Records**

It is the responsibility of the investigator to ensure that a current disposition record of study drug (inventoried and dispensed) is maintained at the study site to include investigational product and the following non-investigational product(s). Records or logs must comply with applicable regulations and guidelines and should include:

- amount received and placed in storage area
- amount currently in storage area
- label identification number or batch number
- amount dispensed to and returned by each subject, including unique subject identifiers

- amount transferred to another area/site for dispensing or storage
- non-study disposition (eg, lost, wasted)
- amount destroyed at study site, if applicable
- amount returned to BMS
- retain samples for bioavailability/bioequivalence, if applicable
- dates and initials of person responsible for Investigational Product dispensing/accountability, as per the Delegation of Authority Form.

BMS will provide forms to facilitate inventory control if the investigational site does not have an established system that meets these requirements.

### **9.2.3 Case Report Forms**

An investigator is required to prepare and maintain adequate and accurate case histories designed to record all observations and other data pertinent to the investigation on each individual treated or entered as a control in the investigation. Data that are derived from source documents and reported on the CRF must be consistent with the source documents or the discrepancies must be explained. Additional clinical information may be collected and analyzed in an effort to enhance understanding of product safety. CRFs may be requested for AEs and/or laboratory abnormalities that are reported or identified during the course of the study.

For sites using the BMS electronic data capture tool, electronic CRFs will be prepared for all data collection fields except for fields specific to SAEs and pregnancy, which will be reported on the paper or electronic SAE form and Pregnancy Surveillance form, respectively. Spaces may be left blank only in those circumstances permitted by study-specific CRF completion guidelines provided by BMS.

The confidentiality of records that could identify subjects must be protected, respecting the privacy and confidentiality rules in accordance with the applicable regulatory requirement(s).

The investigator will maintain a signature sheet to document signatures and initials of all persons authorized to make entries and/or corrections on CRFs.

The completed CRF, including any paper or electronic SAE/pregnancy CRFs, must be promptly reviewed, signed, and dated by the investigator or qualified physician who is a subinvestigator and who is delegated this task on the Delegation of Authority Form. For electronic CRFs, review and approval/signature is completed electronically through the BMS electronic data capture tool. The investigator must retain a copy of the CRFs including records of the changes and corrections.

Each individual electronically signing electronic CRFs must meet BMS training requirements and must only access the BMS electronic data capture tool using the unique user account provided by BMS. User accounts are not to be shared or reassigned to other individuals.

## **9.3 Clinical Study Report and Publications**

A Signatory Investigator must be selected to sign the clinical study report.

For this protocol, the Signatory Investigator will be selected as appropriate based on the following criteria:

- Other criteria (as determined by the study team)

The data collected during this study are confidential and proprietary to BMS. Any publications or abstracts arising from this study require approval by BMS prior to publication or presentation and must adhere to BMS's publication requirements as set forth in the approved clinical trial agreement (CTA). All draft publications, including abstracts or detailed summaries of any proposed presentations, must be submitted to BMS at the earliest practicable time for review, but at any event not less than 30 days before submission or presentation unless otherwise set forth in the CTA. BMS shall have the right to delete any confidential or proprietary information contained in any proposed presentation or abstract and may delay publication for up to 60 days for purposes of filing a patent application.

**10 GLOSSARY OF TERMS**

Term	Definition
Complete Abstinence	
If one form of contraception is required, Complete Abstinence is defined as complete avoidance of heterosexual intercourse and is an acceptable form of contraception for all study drugs. Female subjects must continue to have pregnancy tests. Acceptable alternate methods of highly effective contraception must be discussed in the event that the subject chooses to forego complete abstinence.
 
If two forms of contraception is required, Complete abstinence is defined as complete avoidance of heterosexual intercourse and is an acceptable form of contraception for all study drugs. Subjects who choose complete abstinence are not required to use a second method of contraception, but female subjects must continue to have pregnancy tests. Acceptable alternate methods of highly effective contraception must be discussed in the event that the subject chooses to forego complete abstinence.
 
Expanded definition Complete abstinence as defined as complete avoidance of heterosexual intercourse is an acceptable form of contraception for all study drugs. This also means that abstinence is the preferred and usual lifestyle of the patient. This does not mean periodic abstinence (e.g., calendar, ovulation, symptothermal, profession of abstinence for entry into a clinical trial, post-ovulation methods) and withdrawal, which are not acceptable methods of contraception. Subjects who choose complete abstinence are not required to use a second method of contraception, but female subjects must continue to have pregnancy tests. Acceptable alternate methods of highly effective contraception must be discussed in the event that the subject chooses to forego complete abstinence

**11 LIST OF ABBREVIATIONS**

Term	Definition
ADA	anti-drug antibody
AE	adverse event
ALT	alanine aminotransferase
ANC	absolute neutrophil count
AST	aspartate aminotransferase
AT	aminotransaminases
β-HCG	beta-human chorionic gonadotrophin
BMS	Bristol-Myers Squibb
BP	blood pressure
BUN	blood urea nitrogen
C	Celsius
Ca ++	calcium
CBC	complete blood count
CFR	Code of Federal Regulations
CI	confidence interval
Cl 	chloride
CLcr	creatinine clearance
CLR	renal clearance
CLT	total body clearance
cm	centimeter
CNS	Central nervous system
CRC	Clinical Research Center
CRF	Case Report Form, paper or electronic
CYP	cytochrome p-450
D/C	discontinue
DSM IV	Diagnostic and Statistical Manual of Mental Disorders (4th Edition)
ECG	electrocardiogram
eCRF	Electronic Case Report Form
eg	exempli gratia (for example)

Term	Definition
ESR	Expedited Safety Report
FDA	Food and Drug Administration
FSH	follicle stimulating hormone
g	gram
GCP	Good Clinical Practice
GFR	glomerular filtration rate
h	hour
HBsAg	hepatitis B surface antigen
HBV	hepatitis B virus
HCV	hepatitis C virus
HCO 3 	bicarbonate
HIV	Human Immunodeficiency Virus
HR	heart rate
HRT	hormone replacement therapy
ICD	International Classification of Diseases
ICH	International Conference on Harmonisation
ie	id est (that is)
IEC	Independent Ethics Committee
IMAE	immune-mediated adverse event
IMP	investigational medicinal products
IND	Investigational New Drug Exemption
IRB	Institutional Review Board
IU	International Unit
IV	intravenous
K +	potassium
kg	kilogram
L	liter
LC	liquid chromatography
LDH	lactate dehydrogenase
MDSC	myeloid-derived suppressor cell

Term	Definition
mg	milligram
Mg ++	magnesium
min	minute
mL	milliliter
mmHg	millimeters of mercury
mTOR	mechanistic target of rapamycin
MTD	maximum tolerated dose
µg	microgram
N	number of subjects or observations
Na +	sodium
N/A	not applicable
ng	nanogram
NIMP	non-investigational medicinal products
NSAID	nonsteroidal anti-inflammatory drug
PBMC	peripheral blood mononuclear cell
PO	per os (by mouth route of administration)
PRO	patient reported outcomes
QD, qd	quaque die, once daily
RBC	red blood cell
SAE	serious adverse event
SD	standard deviation
SOP	Standard Operating Procedures
Subj	subject
t	temperature
T	time
TAO	Trial Access Online, the BMS implementation of an EDC capability
TID, tid	ter in die, three times a day
UV	ultraviolet
VEGF	vascular endothelial growth factor
VHL	Von Hippel–Lindau (tumor suppressor gene)

Term	Definition
WBC	white blood cell
WHO	World Health Organization
WOCBP	women of childbearing potential
x g	times gravity

**Research Hypothesis:**

The frequency of high grade (CTCAE v4.0 Grade 3-5) IMAEs observed in patients with advanced or metastatic RCC who are treated with nivolumab monotherapy will not differ from historical adverse event data in this patient population.

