**Table 8.1-1: Estimated Incidence Rates and 95% CIs**

Sample Size	Incidence Rate (%)	Lower 95% CI (%)	Upper 95% CI (%)
150	0.67	0.02	3.66
150	1.0	0.16	4.73
150	2.0	0.41	5.73
150	5.0	2.33	10.24
150	10.0	5.71	15.96
150	11.0	6.74	17.52
150	12.0	7.27	18.30
150	13.0	8.34	19.84
150	14.0	8.88	20.60
150	15.0	9.98	22.11
150	16.0	10.53	22.86
150	17.0	11.65	24.36
150	18.0	12.21	25.10
150	19.0	13.35	26.57
150	20.0	13.92	27.30
150	21.0	15.07	28.76
150	22.0	15.65	29.49
150	23.0	16.82	30.93
150	24.0	17.41	31.65
150	25.0	18.59	33.07

The number of subjects who are evaluable for AEs in the study will be 150. We make the conservative assumption based on Motzer that the rate of IMAEs of grades 3-5 is 13%. The primary goal of the present study is to address whether the rate is consistent with the rate reported in the Motzer study in the sense that the final 95% confidence interval is wholly less than 20%. As indicated in Table 8.1-1, this would happen if the observed rate is less than 13.3% or less (20/150 or fewer grade 3-5 IMAEs). The trial has 61% power to demonstrate consistency of rates in the sense that the probability is 61% of showing the upper bound of the 95% confidence interval is less than 20% when the true rate is 13%. The trial has 80% power to demonstrate the consistency of rates when the true rate is 11.5%

The observed rate may be somewhat larger than 13.3% and will still be consistent with expectations regarding safety, although it may raise concerns that the present population may be different from that of the Motzer study or that the assessment of AEs is different in the two studies. Only if the 95% confidence interval extends beyond 25% would the results of the study raise

serious safety concerns. This would happen if the observed rate is at least 18% (27/150 or more grade 3-5 STRAEs), see [Table 8.1-1](#). Again assuming that the true rate is 13%, the power of the study, the probability that the 95% confidence interval is wholly less than 25% (and so the observed rate is less or equal to 18%) is 95%. Also, if the true rate in the present study is actually 15%, the probability of showing that the 95% confidence interval is wholly less than 25% is 82%.

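### The hypothesis says the high-grade IMAE rate will not differ from history, but the only decision rule is an upper limit of 20%, which does not test that claim in either direction

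*SAP*

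**What the plan says.** The protocol synopsis, protocol 1.4 and the SAP's Research Hypothesis all state that the Grade 3-5 IMAE frequency under nivolumab monotherapy "will not differ from historical adverse event data in this patient population".

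Protocol 8.1, in the text after Table 8.1-1, turns this into a criterion:

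- Sample size: "The number of subjects who are evaluable for AEs in the study will be 150".
- Reference rate, taken from a cited earlier study and described as a conservative assumption: "that the rate of IMAEs of grades 3-5 is 13" (per cent).
- Meaning of consistency with that study: "in the sense that the final 95% confidence interval is wholly less than 20" (per cent).
- Cut-off in events: "this would happen if the observed rate is less than 13.3% or less (20/150 or fewer grade 3-5 IMAEs").
- Operating characteristics: "the probability is 61% of showing the upper bound of the 95% confidence interval is less than 20% when the true rate is 13" (per cent), and "The trial has 80% power to demonstrate the consistency of rates when the true rate is 11.5" (per cent).
- A second threshold, also an upper one: "Only if the 95% confidence interval extends beyond 25% would the results of the study raise" serious safety concerns, which the protocol places at 27 or more events.

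The section raises a possible difference in population or AE assessment only for observed rates above 13.3%. It sets no lower limit and does not require the interval to contain 13%.

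SAP section 5 says the sample size gives enough events for a comparison with historical data. Neither that section nor SAP 7.6.1 carries a rule. SAP 7.6.1 plans a count, a percentage and a tabulation by worst grade.

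**The concern.** A statement that a rate does not differ from a reference points both ways: the rate is neither materially higher nor materially lower. A rule that looks only at the upper confidence limit shows that the rate is below a ceiling. It can be met by a result well below the reference, and it can fail when the data fit the reference well.

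What is at stake is the wording of the conclusion. Under the plan as written, a low count could be reported as agreement with history when the interval excludes the historical figure. A low count is also where a check of definition and ascertainment would be most useful. Protocol 6.2.2 and SAP 7.6.8 count non-endocrine events only if immunosuppressive medication was given, and the documents do not show whether the 13% was obtained under that definition. A reader of the SAP alone meets the hypothesis but not the criterion, and so has only the broader claim to judge the results against.

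**Working it through.** **Inputs (protocol 8.1).** n = 150; reference 13%; consistent if the upper 95% limit is below 20%; serious concern if the interval extends beyond 25%. The interval method is not named. The bounds in Table 8.1-1 match the exact (Clopper-Pearson) method, for example 1/150: 0.02-3.66%; 8/150: 2.33-10.24%; 20/150: 8.34-19.84%.

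**Formulas.** For x events, lower limit = 2.5th percentile of Beta(x, n−x+1) and upper limit = 97.5th percentile of Beta(x+1, n−x). The probability of k or fewer events at true rate p is the binomial sum P(X ≤ k | 150, p).

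**Step 1: reproduce the plan.**
- 20/150: 8.34-19.84%, passes. 21/150: 8.88-20.60%, fails. The cut-off of 20 is right.
- P(X ≤ 20) = 60.7% at 13% (stated 61%) and 80.0% at 11.5% (stated 80%).
- 26/150 has upper limit 24.36% and 27/150 has 25.10%. P(X ≤ 26) = 95.1% at 13% and 82.1% at 15% (stated 95% and 82%).

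All four stated probabilities reproduce.

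**Step 2: where does the interval exclude 13%?**
- Below: 11/150 = 7.33%, interval 3.72-12.74%, excludes 13%. 12/150 = 8.00%, interval 4.20-13.56%, contains it.
- Above: 28/150 = 18.67%, interval 12.78-25.84%, contains 13%. 29/150 = 19.33%, interval 13.35-26.57%, excludes it.

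**Step 3: set the two side by side.**

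| Events in 150 | Interval and 13% | 20% rule |
|---|---|---|
| 0-11 | wholly below | passes |
| 12-20 | contains | passes |
| 21-28 | contains | fails |
| 29 or more | wholly above | fails |

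The first and third rows are the mismatches. Table 8.1-1 contains an example of the first: the row labelled 5.0% has bounds 2.33-10.24%, which exclude 13% and satisfy the rule.

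**Step 4: how often?**

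| True rate | P(0-11) | P(passes, 0-20) |
|---|---|---|
| 13% | 2.0% | 60.7% |
| 11.5% | 6.4% | 80.0% |
| 10% | 17.1% | 92.8% |
| 8% | 45.7% | 99.1% |
| 6% | 80.9% | 99.97% |

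At a true rate of exactly 13% the rule fails 100 − 60.7 = 39.3% of the time. Of this, 1.8 points are 29 or more events, so 37.5 points are 21 to 28 events, whose intervals contain the reference.

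**Step 5: does 11/150 prove a difference from history?** The documents do not give the size of the reference study. Assuming 200 to 1,000 subjects at 13%, two-sided Fisher tests give:
- 11/150 against 26/200, p = 0.11; against 130/1,000, p = 0.06.
- 10/150: p = 0.07 and 0.03.
- 9/150: p = 0.03 and 0.015.

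So 11/150 excludes 13% as a fixed number, but does not show a difference from an estimate of 13%. Over this range, the difference reaches p < 0.05 throughout at 9/150.

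**The case against.** The strongest reply is that the protocol says openly, and in advance, what it means by consistent. The primary objective is to estimate an incidence, the primary analysis is descriptive, and no two-sided test is planned. An upper-only check suits a safety study. Because 13% is called conservative and power is also quoted at 11.5%, the plan allows for a lower rate. For counts just above 20, protocol 8.1 says the result may still fit safety expectations, so missing the 20% criterion is not presented as an alarm.

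Most of this stands. Every passing result that excludes 13% lies below it. The upper limit is a sound criterion and should stay. What does not follow is that meeting it supports the hypothesis as worded.

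Three stronger readings are tempting and are not supported:

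- *That a low rate will usually be mislabelled.* The 81% belongs to a true rate of 6%. That figure is a Grade 3-4 incidence from a Phase 1 trial in mixed malignancies at 0.1 to 10 mg/kg (protocol 8.1), not RCC at the study dose. At the two true rates for which the protocol quotes power under the 20% rule, the probability is 2.0% and 6.4%.
- *That 11/150 demonstrates a difference from history.* This treats 13% as known without error (step 5).
- *That a low count would mean under-reporting.* Nothing in the documents predicts it. AEs are collected continuously and for at least 100 days after the last dose. A difference in definition from the reference study is possible but cannot be checked here.

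**Conclusion.** The point holds as a mismatch between claim and criterion. The 20% rule tests whether incidence is below 20%; it does not test whether incidence differs from the historical rate, in either direction. Results of 0 to 11 events pass with intervals wholly below 13%, and 21 to 28 events fail with intervals containing it. How often the first happens depends strongly on the true rate, from 2.0% at 13% to 81% at 6%.

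A reader might infer that the rule conceals toxicity, or that the power statements are wrong. Neither is so. A reader might also think that meeting the rule shows the rate is not higher than history. It does not: 20/150 passes with an interval reaching 19.84%, well above 13%.

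The figures assume 150 treated subjects, independent subjects with a common event probability, and exact intervals as inferred from Table 8.1-1. Wilson intervals give the same two lower boundaries (11 and 20 events); Wald intervals would move each by one event. The defect limits what may be concluded and does not affect subject safety.

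**What to change.** 1. In the synopsis, protocol 1.4 and the SAP's Research Hypothesis, restate the hypothesis as: *the incidence of Grade 3-5 IMAEs is below 20% (upper limit of the exact two-sided 95% CI below 20%)*.
2. Put the same rule, with the exact method named, into SAP sections 5 and 7.6.1. State it as a confidence limit rather than a count, since the number treated is only approximately 150.
3. Limit the conclusion to incidence below 20%. Do not write that the rate does not differ from, or is not higher than, history.
4. If the interval lies wholly below 13%, report it beside the reference rate. Note that 13% is itself an estimate and that IMAE definition and ascertainment may differ between the studies. Do not describe the result as agreement with history.

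The cost is wording and a slightly narrower claim. Sample size, data collection and the stated 61%, 80%, 95% and 82% probabilities are unchanged.
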